### 10.3.3 Exclusion Criteria

Subjects will be excluded from the study if there is evidence of any of the following criteria at screening or check-in, as appropriate.

1. Subject is mentally or legally incapacitated or has significant emotional problems at the time of the screening visit or expected during the conduct of the study.
2. History or presence of clinically significant medical or psychiatric condition or disease in the opinion of the PI or designee.
3. History of any illness that, in the opinion of the PI or designee, might confound the results of the study or poses an additional risk to the subject by their participation in the study.
4. History or presence of alcoholism or drug abuse within the past 2 years prior to dosing.
5. Consumes 3 units or more of alcohol per day (e.g., 1 unit is equivalent to 240 mL of wine, 1 bottle of beer [12 oz.], or 1 shot of liquor [1 oz.]).
6. History or presence of hypersensitivity or idiosyncratic reaction to the study drug and excipients or related compounds.

7. History or presence of a disease or disorder, acquired or inherited, that is active, or could be reasonably expected to become active during the study, including but not limited to:
  - Hypersensitivity to  $\beta$ -lactam / penicillin derivatives;
  - Bleeding and blood coagulation disorders, including stroke, hemophilias, thrombophilias, or heparin-induced thrombocytopenia;
  - Ischemic disorders, including stroke, heart attack, coronary artery disease;
  - Gastrointestinal disorders, including gastrointestinal bleeds, gallstones, ulcers, diseases or dysfunction of the liver and excluding appendectomy and/or cholecystectomy;
  - Genitourinary disorders, including renal disease;
  - Cardiovascular disorders, including aneurysms, vasculitis;
  - All conditions that are associated with taking medications for pain;
  - Infection of any organ or system within 30 days of dosing;
  - Malignant and cancerous neoplasms of any organ or system;
  - Psychiatric and behavioral disorders;
  - A clinically significant hematological disorder of any type;
  - Inflammation and inflammatory diseases of any organ system.
8. Females of childbearing potential.
9. Females who are pregnant or who are lactating.
10. Positive urine drug or alcohol results at screening or check-in.
11. Positive results at screening for human immunodeficiency virus (HIV), hepatitis B surface antigen (HBsAg), or hepatitis C antibodies (HCV).
12. Supine blood pressure is less than 90/50 mmHg or greater than 140/90 mmHg at screening.
13. Supine heart rate is lower than 40 bpm or higher than 99 bpm at screening.
14. QTcF interval > 450 msec for males or > 460 msec for females, or history of prolonged QT syndrome at screening.
15. Estimated creatinine clearance < 90 mL/minutes at screening using the Cockcroft-Gault estimation.

16. Unable to refrain from or anticipates the use of:

- Any drug, including prescription and non-prescription medications, herbal remedies, or vitamin supplements beginning approximately 14 days prior to dosing and throughout the study.
- Any oral or injectable anticoagulant (e.g., warfarin, heparin, low molecular weight heparin, etc.), coagulants (aprotinin, tranexamic acid, epsilon-aminocaproic acid, and aminomethylbenzoic acid), anti-platelet (e.g., clopidogrel), nonsteroidal anti-inflammatory drugs (NSAIDs) and/or acetylsalicylic acid (ASA) beginning approximately 10 days prior to dosing and throughout the study.
- Any drugs known to be significant inducers of cytochrome P-450 enzymes and/or P-glycoprotein, including St. John's Wort, for 28 days prior to dosing and throughout the study.

Appropriate sources (e.g., Flockhart TableTM) will be consulted to confirm lack of PK/PD interaction with study medication. Acetaminophen (up to 2 g per 24 hour period) or any other treatment of an AE, drug related or not, and considered appropriate and allowable by the PI or designee may be permitted after dosing.

17. Has been on a diet incompatible with the on-study diet, in the opinion of the PI or designee, within the 30 days prior to dosing and throughout the study.
18. Has participated in strenuous exercise or physical activity within 72 hours prior to Day -1, unless deemed acceptable by the PI or designee.
19. Donation of blood or significant blood loss within 56 days prior to dosing.
20. Plasma donation within 7 days prior to dosing.
21. Has been hospitalized within 2 months of Day -1.
22. Participation in another clinical study within 30 days prior to dosing. The 30-day window will be derived from the date of the last blood collection or dosing, whichever is later, in the previous study to Day 1 of the current study.
23. Surgery within the past 90 days prior to dosing which in the opinion of the PI or designee is clinically relevant.
24. Presence of any scars, or tattoos which may obscure the injection site, as deemed by PI or designee.
25. Any condition or circumstance, in the opinion of the PI or designee, which may make the subject unlikely to complete the study or comply with study procedures and requirements, or may pose a risk to the subject's safety.

### 10.3.4 Early Termination of Subjects from the Study

Subject participation in this trial may be discontinued for any of the following reasons:

1. Occurrence of any medical condition or circumstance that exposes the subject to substantial risk and/or does not allow the subject to adhere to the requirements of the protocol.
2. Any SAE, clinically significant AE, severe laboratory abnormality, intercurrent illness, or other medical condition that indicates to the PI or designee that continued participation is not in the best interest of the subject.
3. Subject's decision to withdraw.
4. Requirement of prohibited concomitant medication.
5. Subject failure to comply with protocol requirements or study related procedures.
6. Termination of the study by the Sponsor, FDA, Celerion, or other regulatory authorities.
7. Pregnancy.

The clinical report will include reason(s) for subject withdrawals as well as details relevant to the subject withdrawal. If a subject is withdrawn from the trial prior to study completion, the subject will undergo all procedures scheduled for subjects who terminate early (see [Section 6](#)) as the situation allows (see [Section 10.2.4](#)). Any subject withdrawn due to an AE (whether serious or non-serious) or clinically significant abnormal laboratory test values will be evaluated by the PI or designee or a monitoring physician and will be treated and/or followed up until the symptoms or values return to normal or acceptable levels, as judged by the PI or designee.

Subjects withdrawn may be replaced at the Sponsor's discretion.

### 10.3.5 Study Restrictions

#### 10.3.5.1 Prohibitions and Concomitant Therapy

Consumption of foods and beverages containing the following substances will be prohibited as indicated:

- Xanthines/caffeine: 24 hours before dosing and throughout the period of sample collection (small amounts of caffeine derived from normal foodstuffs e.g., 250 mL/8 oz. decaffeinated coffee or other decaffeinated beverage, per day, with the exception of espresso; 45 g/1.5 oz. chocolate bar, per day, would not be considered a deviation to this restriction);
- Alcohol: 48 hours before dosing and throughout the period of sample collection;

Concomitant therapies will be prohibited as listed in the exclusion criteria in [Section 10.3.3](#).

Acetaminophen (up to 2 g per 24 hour period) or any other treatment of an AE, drug related or not, and considered appropriate and allowable by the PI or designee may be permitted after dosing.

If deviations occur, the PI or designee will decide on a case-by-case basis whether the subject may continue participation in the study based on the time the study medication was administered and its pharmacology.

All medications taken by subjects during the course of the study will be recorded.

### **10.3.5.2 Activity**

Subjects will remain ambulatory or seated upright for the first 4 hours following study medication administration, except when they are supine or semi-reclined for study procedures.

However, should AEs occur at any time, subjects may be placed in an appropriate position.

Subjects will be instructed to refrain from strenuous physical activity which could cause muscle aches or injury, including contact sports at any time within 72 hours prior to Day -1.

## **10.4 Treatments**

### **10.4.1 Treatments Administered**

A separate dosing manual will detail the preparation and treatment administration to be followed for this study.

#### **10.4.1.1 Drug Administration**

E-WE thrombin will be supplied as sterile, non-pyrogenic, preservative-free liquid for IV administration.

E-WE thrombin will be supplied as 0.1 mg/mL for IV use and given as a single IV bolus, according to the planned dose (mcg/kg) for each cohort, as noted below in [Table 1](#).

Matching placebo will be supplied as sterile formulation buffer for injection via IV route.

Drug and placebo will be administered into or distal to the antecubital vein.

An unblinded pharmacist will be responsible for providing E-WE thrombin or placebo to the blinded study personnel for administration as per the randomization scheme.

After evaluation of the sentinel subjects' safety data up to Day 28 by the PI (and SRC if applicable, refer to [Section 10.4.1.4](#)), the remaining group subjects in Cohort 1 will be dosed in two groups separated by at least 14 days (2 subjects in the first group and 2 subjects in the second group).

Subjects dosed on the same day will be dosed with an interval of at least 1 hour between subjects.

All doses will be administered as an IV bolus into a peripheral vein. The time of injection for each dose level and the estimated volumes are outlined below:

**Table 1: Dosing Duration**

Dose Level	Manual Push Time
Cohort 1: 0.5 mcg/kg	~ 15 seconds
Cohort 2: 1.0 mcg/kg	~ 15 seconds
Cohort 3: 2.0 mcg/kg	~ 30 seconds
Cohort 4: 4.0 mcg/kg	~ 1 minute

Dosing will be done while subjects are supine in bed.

The subject weight recorded at check-in will be used to calculate the study drug dose.

The time at which the manual push is started and stopped must be recorded.

#### **10.4.1.2 Planned Dose Levels**

The planned dose levels are as follows:

Cohort 1: 0.5 mcg/kg E-WE thrombin or matching placebo (IV bolus)

Cohort 2: 1.0 mcg/kg E-WE thrombin or matching placebo (IV bolus)

Cohort 3: 2.0 mcg/kg E-WE thrombin or matching placebo (IV bolus)

Cohort 4: 4.0 mcg/kg E-WE thrombin or matching placebo (IV bolus)

Note: The planned dose levels described above may be revised up or down or a dose level may be repeated based upon data from a previous dose level, however, doses will not exceed 4.0 mcg/kg without a protocol amendment.

For Cohort 1 there will be a sentinel group comprised of 2 subjects dosed at least 28 days before the remaining group of subjects; subjects will be randomized in a 1:1 ratio to active and placebo. The remaining subjects in the cohort will be dosed after evaluation of the sentinel subjects' Day 28 safety data and will be dosed in 2 groups separated by at least 14 days (2 subjects in the first group and 2 subjects in the second group). The placebo will be randomized to either group.

The Cohorts 2, 3, and 4 will be dosed in 2 groups separated by at least 14 days (2 subjects in the first group and 3 subjects in the second group). The placebo will be randomized to either group.

Thrombin time and aPTT at Day 14 will be tested to evaluate whether or not subjects may be generating neutralizing antibodies to thrombin/prothrombin. If the thrombin time and aPTTs are normal, the next cohort may be dosed if the rest of the safety data is deemed acceptable by the PI or SRC, as applicable. Confirmation of safety data from the previous cohorts will include for Cohort 1, 6 subjects (4 active and 2 placebo) and for Cohorts 2, 3, and 4, 5 subjects (4 active and 1 placebo).

If thrombin time and/or aPTT are found to be elevated beyond normal range (unless it is still within  $\pm 10\%$  of individual's baseline value at check-in) at Day 14, both tests will be repeated. If aPTT and/or thrombin time are elevated beyond normal range in the retest, a mixing study will be performed. The mixing study will be performed by mixing the subjects' plasma 1:1 with normal human pooled plasma. aPTT and thrombin time will be evaluated. If the aPTT and/or thrombin time do not correct to normal range, the presence of ADA and cross-reacting prothrombin/thrombin antibodies will be presumed, and will be directly assessed before a dose escalation decision.

Any subjects for whom aPTT and/or thrombin time did not reach  $\pm 10\%$  of the baseline value or within the normal range by Day 14, will return every 7 days ( $\pm 2$  days) until aPTT and thrombin time reach  $\pm 10\%$  of the baseline value or within the normal range.

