## 1. PROTOCOL REVISION HISTORY

DATE/NAME	DESCRIPTION
14May2018 by [name]	
Final Protocol, Amendment 2:
 
Following on FDA recommendations, the following changes were made to the protocol:
 

1. The dosing interval between the sentinel group and the remaining subjects was revised to at least 28 days in Cohort 1 and 14 days in the remaining cohorts. The protocol was updated throughout to reflect this change.

2. The following study stopping rules were added to bullet number 5 in Section 10.4.1.4 Dose Escalation and Stopping Rules:

I. <math>\geq 1</math> subject that receive drug in a cohort experience:

a. Life-threatening hypersensitivity reactions (e.g., anaphylaxis, respiratory symptoms, hypotension etc.).

b. Any grade thromboembolic event possibly related to the study drug.

c. Any grade bleeding possibly related to the study drug.

d. Presence of antibodies against human thrombin or prothrombin.

e. Presence of ADA.

DATE/NAME	DESCRIPTION

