#### **10.4.1.4 Dose Escalation and Stopping Rules**

Dose escalation to the next dose level (i.e., next cohort) will not take place until after the PI has reviewed the safety data. If any findings in the safety data are of concern, then the SRC comprised of but not limited to, the Sponsor, medical monitor, and the PI will convene to determine if adequate safety and tolerability from the previous cohort has been demonstrated to permit proceeding to the next cohort. The SRC review of all pertinent blinded safety/tolerability data must comprise of physical examinations, ECGs, vital signs, clinical laboratory tests [including coagulation], thrombin time, injection site reaction, and AEs available for all subjects who have completed up to Day 14 procedures.

Data from all subjects in the cohort will be used and reviewed for a dose escalation decision and a minimum of 4 subjects must complete the study (up to Day 14) before proceeding to the next higher dosing cohort.

Together they will make one of the following determinations:

1. To continue with the study as planned.
2. To continue with the study and add additional safety evaluations.
3. To continue with the study and repeat a cohort.

4. To continue with the study by adjusting to an intermediate dose between the current dose and the previous lower dose (i.e., add an additional cohort) or to repeat a cohort, if:
  - a. At least 1 subject has a SAE or visit to the emergency room deemed to be possibly study drug related (see [Section 11.1.8.4](#)).
  - b. At least 25% of subjects in a cohort experience a grade  $\geq 2$  AE deemed to be possibly related to the study drug.
5. To stop the study. The study will be terminated if the following number of subjects meet any of the following criteria and the subjects were determined to have received active drug after unblinding:
  - I.  $\geq 1$  subject that receive drug in a cohort experience:
    - a. Life-threatening hypersensitivity reactions (e.g., anaphylaxis, respiratory symptoms, hypotension etc.).
    - b. Any grade thromboembolic event possibly related to the study drug.
    - c. Any grade bleeding possibly related to the study drug.
    - d. Presence of antibodies against human thrombin or prothrombin.
    - e. Presence of ADA.
  - II.  $\geq 2$  subjects that receive drug in a cohort:
    - a. Has a drug possibly or probably related SAE (see [Section 11.1.8.4](#)).
    - b. Experiences a drug related grade  $\geq 3$  toxicity (see [Section 11.1.8.3](#)).

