
Cohorts will be staggered to allow sufficient time for adequate review of safety and tolerability from the prior cohort.

Safety aPTT, PT, and thrombin time data from a cohort will be needed for a dose escalation decision. If aPTT and thrombin time are elevated at Day 14, a mixing study will be performed. If the mixing study does not normalize the aPTT and/or thrombin time, dose escalation will be postponed until ADA data is available. If either ADA assay are confirmed to be positive, the study will be stopped according to the dose escalation and stopping rules outlined above. APC-PCI complex level data will not be needed for a dose escalation decision.

When applicable, a written statement fully documenting the reasons for study termination will be provided to the IRB.

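### No rule makes a cohort's second group wait for review of the first group's Day 14 data, and the pending-ADA hold stops only dose escalation

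*Protocol*

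**What the plan says.** **Dosing within a cohort.** In Cohort 1, the subjects after the sentinel pair are dosed only once the sentinels' Day 28 safety data have been evaluated (Protocol 10.4.1.1 and 10.4.1.2). The investigator does this, with the Safety Review Committee (SRC) if applicable. For the other cohorts, 10.4.1.2 gives an interval and no review: "The Cohorts 2, 3, and 4 will be dosed in 2 groups separated by at least 14 days". The Synopsis, flow chart footnotes c and k, 10.1, 10.3.1, 10.4.3 and SAP section 3 likewise give only the interval. The revision history lists the interval among changes made after FDA recommendations.

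**What the Day 14 results control.** If aPTT and thrombin time are normal, "the next cohort may be dosed if the rest of the safety data is deemed acceptable by the PI or SRC" (10.4.1.2). If they are raised on retest, a mixing study is done that day. If it does not correct, antibodies are presumed and "will be directly assessed before a dose escalation decision" (10.4.1.2). Section 10.4.1.4 adds: "If the mixing study does not normalize the aPTT and/or thrombin time, dose escalation will be postponed until ADA data is available". Investigator review in 10.4.1.4, and SRC review in 10.4.1.4, 10.4.4.3 and SAP 4.2, likewise precede escalation.

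**Stopping rules (10.4.1.4, item 5).** One subject on active drug is enough to end the study for several events. These include "Presence of antibodies against human thrombin or prothrombin" and the presence of ADA, provided "the subjects were determined to have received active drug after unblinding". The later text of the same section ties the ADA stop to a confirmed positive assay.

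**The concern.** The 14-day spacing looks designed so that the first group's clotting screen can inform the second group's dosing, but the text never makes that connection. The gap matters most after an uncorrected mixing study. The protocol then presumes antibodies to the drug and cross-reacting antibodies to thrombin or prothrombin, and withholds a higher dose until the ADA result arrives. It says nothing about giving the same dose to the next two or three subjects in the cohort.

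The sentinel step does not fill this gap. It covers one active subject at 0.5 mcg/kg, a dose that section 8.3.2 expects to have little or no biological effect. There is no equivalent review at 1.0, 2.0 or 4.0 mcg/kg.

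**Working it through.** **Inputs.** Cohort 1 has 6 subjects (4 active, 2 placebo). Cohorts 2-4 have 5 each (4 active, 1 placebo), dosed as 2 then 3, with the placebo randomised to either group (10.3.1, 10.4.3). Groups are at least 14 days apart. Dosing is on Day 1, check-in on Day -1, and the clotting screen on Day 14. At least 4 subjects must complete Day 14 before escalation (10.4.1.4). The dose ceiling without an amendment is 4.0 mcg/kg (10.4.1.3).

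**Plan's own figure.** 6 + 3 × 5 = 21 subjects, as stated in 10.3.1. Planned actives are 4 × 4 = 16.

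**Timing in Cohorts 2-4, on first-group days**
- Earliest second-group dose: Day 1 + 14 days = Day 15.
- Earliest second-group check-in: the day before, Day 14. This is also the day of the first group's screen and any mixing study.
- Earliest second-group Day 14: Day 15 + 13 = Day 28.
- The earliest escalation review with 4 completers is therefore Day 28, 13 days after the second group may be dosed.

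**Can the escalation hold protect the second group?** Completers required, 4, less first-group subjects, 2, leaves at least 2 from the second group. An escalation decision therefore cannot arise until at least 2 second-group subjects have been dosed and followed to Day 14. In Cohort 4 no higher dose is planned, so the hold has nothing to act on.

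**Who is covered by the gap**
- Second groups in Cohorts 2-4: 3 × 3 = 9 of 15 subjects.
- Actives per second group: 2 if it contains the placebo, otherwise 3. Over three cohorts this is 6 to 9.
- Share of the 12 actives in Cohorts 2-4: 6/12 = 50% to 9/12 = 75%. Share of all 16 planned actives: 6/16 = 37.5% to 9/16 = 56.3%.
- Expected actives if the placebo is equally likely in any of 5 positions: (0.6 × 2 + 0.4 × 3) × 3 = 7.2. If it is equally likely in either group: (0.5 × 2 + 0.5 × 3) × 3 = 7.5.
- At 4.0 mcg/kg: 2 or 3 actives.
- Cohort 1's last group adds 2 subjects, 1 or 2 of them active. They have the sentinel review behind them but no required review of the pair dosed just before them.

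**Do the stopping rules cover a pending result?** A failed mixing study leads to a presumption of antibodies. Item 5 of 10.4.1.4 refers to presence and requires that the subject be found to be on active drug. The later text of that section stops the study on a confirmed positive assay. Whether a presumed antibody stops the study is therefore unclear. The ADA turnaround is not stated, so the result may still be pending on Day 15.

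**The case against.** The strongest reply is that the exceptions leave only a narrow window. The stopping rules apply at every dose and are strict: one related bleed or thromboembolic event of any grade in an active subject ends the study. After an uncorrected mixing study the protocol presumes the presence of antibodies, and presence is also the word in the stopping rule, so a stop can be argued. Section 10.4.1.4 concerns when escalation waits, and its silence on same-dose dosing is not permission. The affected subject stays in the unit until the results are known (10.2.4), so the site would know of the signal and the investigator would have to proceed knowingly. A general review before every second group also imposes a delay when there is no signal.

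Much of this is fair. A careful investigator would probably pause, and the sponsor or the CRO can end the study at any time (13.2). Section 11.1.8.2 is weaker support: it requires the investigator to evaluate and follow adverse events and significant laboratory values, but gives no power to halt dosing. The argument from presence does not settle the matter, given the confirmed-assay wording and the unblinding condition. The protocol also chose a mandatory hold over discretion before escalation, and the same signal bears directly on giving again the dose that produced it. Section 10.4.1 mentions a separate dosing manual, which is not among the documents available here.

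**Conclusion.** The concern holds. The only review required before further dosing within a cohort is the Cohort 1 sentinel evaluation. Each Day 14 control, including the pending-ADA hold, acts on escalation or the next cohort. Read literally, the plan does not stop same-dose dosing of 6 to 9 active subjects across Cohorts 2-4, including 2 or 3 at 4.0 mcg/kg, while the first group's Day 14 results are unreviewed or an ADA result is pending.

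These counts follow from the planned group sizes and the minimum interval. They describe who is covered by the gap and are not a risk: the documents give no probability of a failed mixing study and no assay turnaround. This is a missing rule, not a prediction that anyone would keep dosing. It should be corrected because the remedy is cheap and the protocol itself treats these antibodies as grounds for ending the study.

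**What to change.** 1. In Protocol 10.4.1.2 and 10.4.1.4, require a documented investigator review, with the SRC if there are concerns, of first-group safety, aPTT and thrombin time data through Day 14 before the second group of each cohort is dosed. Mirror this in the Synopsis, flow chart footnotes c and k, 10.1, 10.3.1, 10.4.1.1, 10.4.3 and SAP section 3.
2. In 10.4.1.4, widen the pending-ADA hold from dose escalation to all further dosing, naming the second group of the same cohort. This covers Cohort 4 and means that the unclear stopping wording no longer decides whether the second group is dosed.

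The second edit alone closes the pending-antibody window. The first also covers the rest of the Day 14 safety data. The clinical release criteria remain for the sponsor and investigator to set.

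**Cost.** Amendment wording and one review per cohort of data already collected, with no change to sample size, assessments or analyses. Expect a short delay per cohort, because second-group check-in can fall on the day of the first group's screen. Waiting for an ADA result takes longer and may mean rescreening or replacing subjects whose 28-day screening window (10.2.1) lapses. The time a subject can wait is 28 minus the days from screening to planned dosing. For assumed intervals of 7, 14, 21 and 28 days, that leaves 21, 14, 7 and 0 days.
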